6.12. Safety Analysis	28
6.12.1. Drug Exposure	29
6.12.2. AEs	29
6.12.3. Laboratory Tests	30
6.12.4. Vital Signs	30
6.12.5. Physical Examination	30
6.12.6. 12-lead ECG	31
6.13. Other Evaluations	31
6.14. Sub-group Analysis	31
7. Interim Analysis	32
8. Changes to the Planned Analysis of the Protocol	32
9. References	32
10. Statistical Chart Templates and Dataset Programming Specifications	32
10.1. Statistical Chart Template	32
10.2. Dataset Programming Specifications	32

11. Appendices	32
11.1. Appendix A Multiple Imputation (MI) Method	32

List of Abbreviations and Definitions of Terms

Abbreviations/Terms	Full Name
AE	Adverse Event
ALT	Alanine Aminotransferase
ANCOVA	Analysis of Covariance
ANOVA	Analysis of Variance
ASMI	Appendicular Skeletal Muscle Index
AST	Aspartate Aminotransferase
ATC	Anatomical Therapeutic Chemical Classification
ATC2	ATC Level 2 Terminology
BMI	Body Mass Index
Ccr	Creatinine Clearance
CI	Confidence Interval
CTCAE	Common Terminology Criteria for Adverse Events
DXA	Dual-energy X-ray Absorptiometry
ECG	Electrocardiogram
eCRF	Electronic Case Report Form
FAS	Full Analysis Set
GFAP	Glial Fibrillary Acidic Protein
IFN	Interferon
IL	Interleukin
LOCF	Last Observation Carried Forward
Max	Maximum
MDS-UPDRS	Unified Parkinson's Disease Rating Scale
MedDRA	Medical Dictionary for Regulatory Activities
Median	Median
MI	Multiple Imputation
Min	Minimum
MMRM	Mixed-Effects Model for Repeated Measures
NCI	National Cancer Institute

PD	Parkinson's Disease
PN	Preferred Name
PPS	Per-Protocol Set
PT	Preferred Term
Q1	First Quartile
Q3	Third Quartile
SAE	Serious Adverse Event
SAP	Statistical Analysis Plan
SD	Standard Deviation
SOC	System Organ Class
SS	Safety Set
TBIL	Total Bilirubin
TEAE	Treatment-Emergent Adverse Event
TNF	Tumor Necrosis Factor
TRAЕ	Treatment Related Adverse Event
ULN	Upper Limit of Normal
WHODrug	World Health Organization Drug Dictionary

1. Introduction

This Statistical Analysis Plan is prepared for study entitled as "A Randomized, Double-blind, Placebo Parallel-controlled Phase II Clinical Trial to Evaluate the Efficacy and Safety of TJ0113 Capsules in Patients with Early Parkinson's Disease" (Protocol No.: TJJS01-201). It provides a detailed description of the statistical analysis content and methodology.

This statistical analysis plan is developed based on the study protocol version 4.0 dated February 11, 2025, and the case report form (CRF) version 4.0 dated April 28, 2025.

2. Study Design

2.1. Overall Design

This study is a randomized, double-blind, placebo parallel-controlled Phase II clinical trial designed to evaluate the efficacy and safety of TJ0113 capsules in patients with early-stage PD. It is planned to include approximately 150 subjects with early-stage PD who will be randomized in a 1:1 ratio into two cohorts (Cohort 1: 200 mg dose group; Cohort 2: 400 mg dose group). Within each cohort, subjects who have been successfully screened will be randomly assigned to TJ0113 capsules group and the placebo group in a ratio of 2:1 within each stratum based on a stratification factor whether they have been receiving levodopa, the background medication for PD (yes vs. no) at a stable dose. Among them, approximately 50 subjects will receive TJ0113 capsules and approximately 25 subjects will receive the placebo. In this study, there will be approximately 50 subjects in each of the TJ0113 capsules 200 mg group, TJ0113 capsules 400 mg group and the placebo group.

After randomization, subjects will receive the oral administration of TJ0113 capsules or the placebo for 12 consecutive weeks and continue to receive follow-up visits for 1 week (telephone follow-up) after the end of treatment. For subjects who have been receiving the anti-PD drug at a stable dose for at least 4 weeks prior to study entry, the original regimen of the background medication for PD should be maintained during the study.

The trial period includes a screening phase (up to 4 weeks), a treatment phase (12 weeks), and a follow-up phase (1 week, via telephone follow-up).

2.2. Randomization and Blinding

This study is a randomized, double-blind, placebo parallel-controlled Phase II clinical trial. The subject randomization numbers and drug randomization numbers will be pre-generated by the randomization statistician (independent of the project) in the statistical department, to create the randomization table. The detailed randomization procedure will be described in the randomization plan.

Throughout the study, all personnel involved in blinding should remain blinded until the database is locked. Refer to Section 5.3.2 of the protocol for the detailed blinding procedure.

3. Study Objectives and Endpoints

Trial Objectives	Trial Endpoints
Primary Objective	Primary Endpoint
Secondary Objectives	Secondary Endpoints

To assess the efficacy of TJ0113 capsules in the treatment of patients with early-stage PD.
	
Changes from baseline in scores of the Unified Parkinson's Disease Rating Scale (MDS-UPDRS) Part III (motor examination) in subjects after 12 weeks of treatment. Evaluation time point: ≥ 12 hours from the most recent dose of anti-PD drug.
 
 Changes from baseline in scores of MDS-UPDRS Part III (motor examination) in subjects after 1, 4, 8 weeks of treatment. Evaluation time point at each visit: ≥ 12 hours from the most recent dose of anti-PD drug; Changes from baseline in scores of MDS-UPDRS Part III (motor examination) in subjects after 1, 4, 8, 12 weeks of treatment. Evaluation time point at each visit: 2 ± 1 hours from the most recent dose of anti-PD drug; Changes from baseline in scores of MDS-UPDRS Part I, II and IV in subjects after 1, 4, 8 and 12 weeks of treatment; Changes from baseline in the total scores of MDS-UPDRS in subjects after 1, 4, 8, 12 weeks of treatment, including: 
 Total score 1: II+III; wherein, the evaluation time point for MDS-UPDRS Part III (motor examination) is ≥ 12 hours from the most recent dose of anti-PD drug; Total score 2: II+III; wherein, the evaluation time point for MDS-UPDRS Part III (motor examination) is 2 ± 1 hours from the most recent dose of anti-PD drug; Total score 3: I+II+III; wherein, the evaluation time point for MDS-UPDRS Part III (motor examination) is ≥ 12 hours from the most recent dose of anti-PD drug; Total score 4: I+II+III; wherein, the evaluation time point for MDS-UPDRS Part III (motor examination) is 2 ± 1 hours from the most recent dose of anti-PD drug;

	
 - Total score 5: I+II+III+IV; wherein, the evaluation time point for MDS-UPDRS Part III (motor examination) is ≥ 12 hours from the most recent dose of anti-PD drug; - Total score 6: I+II+III+IV; wherein, the evaluation time point for MDS-UPDRS Part III (motor examination) is 2 ± 1 hours from the most recent dose of anti-PD drug.

To assess the safety of TJ0113 capsules in the treatment of patients with early-stage PD.
	
 • AE; • Laboratory test; • Vital signs; • Physical examination; • 12-lead ECG.
Exploratory Objectives	Exploratory Endpoints

To explore the changes in inflammatory indicators in early-stage PD patients treated with TJ0113 capsules.
	Changes in inflammatory markers from baseline at 4, 8, and 12 weeks of treatment.

To investigate the impact of TJ0113 capsules on PD biomarkers in early-stage PD patients.
	Changes in α -synuclein and glial fibrillary acidic protein (GFAP) from baseline after 12 weeks of treatment.

To explore the effect of TJ0113 capsules on skeletal muscle mass and function in early-stage PD patients.
	
 • Changes from baseline in appendicular skeletal muscle mass index (ASMI) measured by dual-energy X-ray absorptiometry (DXA) after 12 weeks of treatment; • Changes from baseline in muscle strength (grip strength) after 12 weeks of treatment; • Changes from baseline in 6-meter walking speed test after 12 weeks of treatment.

To explore the association between the efficacy of TJ0113 capsules and the genomic characteristics in early-stage PD patients.
	The association between the efficacy of TJ0113 capsules and the genomic characteristics in early-stage PD patients.

3.1. Estimand

The primary estimands of this study are as follows:

- Population: Early-stage PD patients who meet the inclusion criteria (refer to Section 4.1 of the protocol) and do not meet the exclusion criteria (refer to Section 4.2 of the protocol).
- Treatment: Patients will be randomized into one of two cohorts (200 mg and 400 mg dose groups) in a 1:1 ratio. Within each cohort, patients will be further randomized in a 2:1 ratio to receive either TJ0113 capsules or placebo.
- Endpoint: Change from baseline in the Movement Disorder Society-Unified Parkinson's Disease Rating Scale (MDS-UPDRS) Part III (Motor Examination) score after 12 weeks of treatment. Evaluation time point: \geq 12 hours from the most recent dose of anti-PD drug.
- Concomitant Events and Management Strategies: Any concomitant medications (excluding the investigational product and stable anti-PD drugs at enrollment) or treatments that may affect the PD progression will be addressed using therapeutic strategies.
- Population-level Summary: Least squares mean difference in the change from baseline in MDS-UPDRS Part III (Motor Examination) scores between the TJ0113 capsule group and the placebo group after 12 weeks of treatment. Evaluation time point: \geq 12 hours from the most recent dose of anti-PD drug. (Refer to Section [6.10.1.1](#))

3.2. Efficacy Endpoints

MDS-UPDRS

The MDS-UPDRS consists of four parts: Part I (Nonmotor Experiences of Daily Living), Part II (Motor Experiences of Daily Living), Part III (Motor Examination), and Part IV (Motor Complications). Throughout the study, each subject should have a fixed rater to evaluate his/her score using MDS-UPDRS.

➤ For subjects who have received the anti-PD drug at a stable dose for at least 4 weeks prior to study entry, the MDS-UPDRS assessment time points and corresponding assessment parts are as follows:

Visit	MDS-UPDRS assessment part	Assessment time points
V1	Part I	No special requirements
	Part III	Before administration of background medication for PD (\geq 12 hours from the most recent dose of the background medication for PD)
V2, Early Withdrawal	Part III	Before administration of background medication for PD (\geq 12 hours from the most recent dose of the background

Visit (if applicable)		medication for PD)
		After administration of background medication for PD (to be performed at 2 ± 1 hours after the administration of background medication for PD at this visit)
		Parts I, II, and IV
V3~V6	Part III	Before administration of the investigational product and the background medication for PD (≥ 12 hours from the most recent administration of background medication for PD and the investigational product)
		After administration of the investigational product and the background medication for PD (to be performed at 2 ± 1 hours after the administration of the background medication for PD and the investigational product at this visit)
		Parts I, II, and IV

- For subjects who have not received the anti-PD drug at study entry, the MDS-UPDRS assessment time points and corresponding assessment parts are as follows:

Visit	MDS-UPDRS assessment part	Assessment time points
V1	Part I	No special requirements
	Part III	No special requirements
V2	Part III	No special requirements
	Parts I, II, and IV	No special requirements
V3~V6	Part III	Before administration of the investigational product (≥ 12 hours from the most recent administration of the investigational product)
		After administration of the investigational product (to be performed at 2 ± 1 hours after the administration of the investigational product at this visit)

Visit	MDS-UPDRS assessment part	Assessment time points
	Parts I, II, and IV	No special requirements
Early Withdrawal Visit (if applicable)	Part III	\geq 12 hours from the most recent administration of the investigational product
	Parts I, II, and IV	No special requirements

3.3. Safety Endpoints

3.3.1. AEs

Adverse Event (AE)

The definition of adverse events collected in this study will be detailed in Section 9 of the protocol. Specific information such as the start date, end date, and severity of adverse events will be recorded in detail on the adverse event page of the eCRF.

Treatment-Emergent Adverse Event (TEAE)

TEAE will be defined as any adverse event that newly occurs (not present before treatment) or worsens relative to pretreatment after the first administration of the investigational product.

Treatment-related Adverse Event (TRAE)

TRAE will be defined as a TEAE assessed by the investigator as related to the investigational product, including "definitely related," "probably related," or "possibly related." The relationship to the investigational product will be recorded in the eCRF adverse event page.

Serious Adverse Event (SAE)

The definition of serious adverse events (SAEs) will be detailed in Section 9.1.4 of the protocol. Investigators will determine whether an event qualifies as an SAE. Information such as the occurrence date of the SAE and the criteria met will be recorded in the adverse event page of the eCRF.

Adverse Event Grading

The severity of AEs will be recorded according to the National Cancer Institute (NCI) Common Terminology Criteria for Adverse Events (CTCAE) Version 5.0. The CTCAE grade of adverse events will be determined by the investigator and recorded in the eCRF.

Adverse Events Leading to Dose Interruption, Dose Reduction, or Discontinuation

The actions taken for adverse events that will be recorded in the eCRF adverse event page include dose suspension, dose reduction, and discontinuation.

Death

Any death due to adverse events will be recorded in the adverse event page of the eCRF. In addition, detailed information on deaths will be recorded in the death page of the eCRF, including the date of death and cause of death.

3.3.2. Laboratory Tests

Including hematology, blood biochemistry, urinalysis, coagulation function, serum pregnancy test, urine pregnancy test, etc. The laboratory tests collected in the eCRF are listed in Table 1.

Table 1 Laboratory Test Items

Items	Examination Indicators
Hematology (CBC)	White blood cell count, absolute neutrophil count, neutrophil percentage, absolute lymphocyte count, lymphocyte percentage, absolute monocyte count, monocyte percentage, absolute eosinophil count, eosinophil percentage, absolute basophil count, basophil percentage, red blood cell count, hemoglobin, hematocrit, mean corpuscular volume, mean corpuscular hemoglobin, mean corpuscular hemoglobin concentration, red cell distribution width, platelet count, mean platelet volume, plateletcrit, and platelet distribution width
Blood Biochemistry	Fasting blood glucose, bile acid, total protein, albumin, globulin, albumin/globulin ratio, TBIL, direct bilirubin, indirect bilirubin, ALT, AST, γ -glutamyl transferase, alkaline phosphatase, lactate dehydrogenase, creatine kinase, creatine kinase-MB, urea/urea nitrogen, serum uric acid, creatinine, potassium, sodium, chloride, calcium, magnesium, inorganic phosphorus, triglycerides, total cholesterol, high-density lipoprotein cholesterol, and low-density lipoprotein cholesterol.
Creatinine clearance rate (Ccr)	Calculate Ccr based on body weight measurements and serum creatinine levels in blood biochemistry tests.
Urinalysis	Glucose urine, bilirubin urine, urine ketone body, urine pH, protein urine, urine urobilinogen, nitrite urine, occult blood urine, white blood cells urine, red blood cells urine, microscopic examination of urine sediment (red blood cells, white blood cells), and specific gravity urine.
Coagulation function	Prothrombin time, activated partial thromboplastin time, thrombin time, international normalized ratio, and fibrinogen
Pregnancy Test	Serum pregnancy and urine pregnancy

3.3.3. Vital Signs

Including respiration, pulse, body temperature, systolic blood pressure, and diastolic blood pressure.
 Statistical Analysis Plan Version 1.0

3.3.4. Physical Examination

It includes skin and mucous membranes, lymph nodes, head, neck, chest, abdomen, spine and limbs, nervous system and mental state.

3.3.5. 12-lead ECG

The parameters include: heart rate, PR interval, QRS complex duration, uncorrected QT interval, and Fridericia-corrected QTc (QTcF). Two measurements will be taken within 20 minutes, and the average value is calculated and rounded to the nearest integer.

3.4. Exploratory Endpoints

3.4.1. Inflammatory Markers

The exploratory inflammatory indicators of this study include interleukin (IL)-1 β , IL-2, IL-4, IL-5, IL-6, IL-8, IL-10, IL-12p70, IL-17A, interferon (IFN)- α , IFN- γ , and tumor necrosis factor (TNF)- α . The specific testing indicators should be determined based on the actual implementation at each center.

3.4.2. PD Biomarkers

The exploratory PD biomarker measures in this trial include α -synuclein and GFAP.

3.4.3. Assessment of Skeletal Muscle Mass and Function

The exploratory skeletal muscle mass and function assessment indicators in this trial include ASMI, muscle strength (handgrip strength), and the 6-meter walk test. The specific testing indicators should be determined based on the actual operations of each center.

4. Sample Size

The sample size of this study is not determined based on the formal statistical assumptions and it is expected to include approximately 150 subjects with early-stage PD, who will be randomized in a 1:1 ratio into two cohorts (Cohort 1: 200 mg dose group; Cohort 2: 400 mg dose group). Within each cohort, the subjects will be randomized into the TJ0113 capsules group and the placebo group in a ratio of 2:1, with approximately 50 subjects receiving TJ0113 capsules and approximately 25 subjects receiving the placebo. In this study, there will be approximately 50 subjects in each of the TJ0113 capsules 200 mg group, TJ0113 capsules 400 mg group and the placebo group.

5. Analysis Sets

Full analysis set (FAS): including all randomized subjects who have received at least one dose of investigational product.

Per-protocol set (PPS): including subjects in the FAS who have not experienced major protocol deviations that affect the primary efficacy endpoint.

Safety Set (SS): Includes all subjects who received at least one dose of the investigational product and underwent at least one post-dose safety assessment.

Demographics and baseline characteristics will be analyzed based on FAS, the efficacy analyses will be performed based on both FAS and PPS, and the safety analyses will be performed based on SS.

6. Statistical Analysis Methods

6.1. Statistical Considerations

Statistical analyses will be performed using SAS 9.4 or higher, with results reported in summary tables or subject listings. In the subject list, the subject screening number serves as the universal unique identifier for subjects in this study, and the default sorting will be based on the subject screening number.

Continuous Variables

For continuous variables, unless otherwise specified, the following descriptive statistics will be used for summarization: number of subjects, mean (Mean), standard deviation (SD), median (Median), first quartile (Q1), third quartile (Q3), minimum (Min), and maximum (Max). The measurement precision of each continuous variable will be used to determine the number of decimal places displayed in tables, charts, and listings. The decimal places for minimum and maximum will remain consistent with the original data recorded in the database; means and quantiles will retain one additional decimal place compared to the original data in the database; standard deviations will retain two additional decimal places compared to the original data in the database. Any values requiring conversion to standard units should adhere to the aforementioned principles after being converted to the corresponding precision values. When determining the number of decimal places to display, both the validity of precision and the practicality of presentation will be considered. For example, if there are too many decimal places to accommodate additional information, the reported data will retain an appropriate number of decimal places, up to a maximum of four.

Categorical Variable

For categorical variables, the number and percentage of subjects will be summarized. Unless otherwise specified, percentages will be calculated based on all subjects in the respective analysis population. Percentages will be rounded to one decimal place. When the percentage is 100%, it will be reported as 100%. If the number of subjects is 0, the percentage will not be reported.

General Principles of Statistical Inference

A Mixed Model for Repeated Measures (MMRM) will be used to calculate nominal P values for between-group comparisons of primary and secondary endpoints; where applicable, analysis of covariance (ANCOVA) will be employed to calculate nominal P values for between-group comparisons of primary endpoints. For exploratory endpoints with normally distributed variables, analysis of variance (ANOVA) will be used to calculate nominal P-values for between-group comparisons; otherwise, the Wilcoxon rank-sum test will be employed for between-group comparisons to calculate nominal P-values.

Confidence Interval (CI)

Unless otherwise specified, the CI refers to a two-sided 95% CI, with one more decimal place than the derived data or parameters.

P-value

This study does not conduct formal hypothesis testing, and the summarized P-values will be nominal P-values. P-values should be retained to 4 decimal places. If the P-value is less than 0.0001, it should be presented as "<.0001"; if the P-value will be greater than 0.9999, it should be presented as ">.9999".

Treatment Group

Unless otherwise specified, it will be summarized by the TJ0113 capsules 200 mg group, TJ0113 capsules 400 mg group, and the placebo group.

Study Day 1

Study Day 1 is defined as the day of the first dose of the investigational product. All safety and efficacy assessments will be calculated based on Study Day 1.

- If the visit date \geq the first dose date, then: Study day = Visit date - First dose date + 1
- If the visit date $<$ the first dose date, then: Study day = Visit date - First dose date.

There is no definition of Study Day 0 in this study.

Repeated Measurements or Assessments

If more than one measurement or assessment of a certain parameter is conducted at the same time point during the same visit according to the study protocol, it will be defined as a repeated measurement or assessment. The mean value of repeated measurements or evaluations will be used as the analytical value. In this study, all 12-lead electrocardiogram (ECG) parameters will be measured twice, and clinical evaluations will be performed with duplicate assessments.

Baseline Value

Unless otherwise specified, baseline is defined as the last valid measurement or assessment result prior to the first dose (including scheduled or unscheduled visits). If an unscheduled visit date coincides with the scheduled visit date and the exact time is unknown, the results from the scheduled visit should be used as the baseline.

For repeated measurements (e.g., duplicate ECG measurements), the mean of the repeated measurements will be used as the baseline value in the analysis.

For the MDS-UPDRS Part III (Motor Examination) score, if the assessment time point is \geq 12 hours after the last dose of anti-PD medication, the last valid assessment result corresponding to the " \geq 12 hours after the last dose of anti-PD medication" time point prior to the first dose will be used as the baseline value in the analysis. If the assessment time point is 2 ± 1 hours after the last dose of anti-PD medication, the last valid assessment result corresponding to the " 2 ± 1 hours after the last dose of anti-PD medication" time point prior to the first dose will be used as the baseline value in the analysis.

For the MDS-UPDRS Parts I, II, and IV scores, the last valid assessment result prior to the first dose will be used as the baseline value for analysis.

Change from Baseline

Change from baseline = Post-baseline measurement - Baseline value.

Analysis Visit

Analysis visits include: Baseline, V3 (Week 1 of treatment), V4 (Week 4 of treatment), V5 (Week 8 of treatment), V6 (Week 12 of treatment).

Unscheduled Visit

For safety analysis tables summarized by visit, only scheduled visits are included. Unless otherwise specified, data from unscheduled visits will be included in the following analyses:

- Calculate baseline values
- Analyses involving abnormalities and clinically significant findings
- Listing

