## 2.5 Benefit/Potential Risk Assessment

### 2.5.1 Risk Assessment

Based on the results of the toxicological studies and the guidance of drug clinical trial approval letter (No. 2023LP01405), TJ0113 capsules were generally well tolerated. The main toxicities were gastrointestinal toxicity (vomiting, loose stools), renal toxicity (basophilic lesions in renal tubules), hepatotoxicity (total bilirubin [TBIL] increased, liver coefficient increased), potential impact on QT interval, and embryo-fetal reproductive toxicity, etc. Based on the completed phase I clinical trial in healthy subjects (registration No.: CTR20232426), the safety profile of TJ0113 capsules following the single dose administration within the dose range of 80-720 mg, and that following the multiple dose administration at 200 mg QD, 400 mg QD, and 300 mg BID was good; the incidences of AEs were similar between the treatment group and the placebo group, and no unexpected or serious safety signals have been identified.

In the phase II study, in order to minimize the overall risk of subjects and ensure the safety of subjects, the following measures were taken: enrollment of appropriate subject population based on the inclusion/exclusion criteria, conducting the screening examinations/tests (medical history and treatment history, vital signs, physical examination, laboratory tests, serum virology test, 12-lead electrocardiogram [ECG], etc.), and safety evaluation and follow-up. This study will also strictly require the subjects to take highly effective contraceptive measures and conduct regular pregnancy tests for women of childbearing potential. In addition, all subjects will be closely monitored for clinical safety assessments such as vital signs, laboratory tests, 12-lead ECG, etc. according to schedule of activities (SoA). Therefore, it can be considered that the expected risks of TJ0113 capsules in the phase II study is controllable.

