### **8.7.4 Early Withdrawal Visit**

Subjects who have early withdrawn from the study should complete the early withdrawal visit within 7 days after the investigator's awareness (if it is less than 7 days from the date of the

previous visit, repeated tests of the same item can be waived), excluding subjects who have early withdrawn from the study due to withdrawal of consent or are lost to the follow-up.

At the early withdrawal visit, the following procedures will be performed:

- Subjects must be fasted before each visit (fast for at least 10 hours overnight without depriving of water);
- Vital signs;
- Physical examination;
- 12-lead ECG;
- Laboratory tests: including hematology, blood chemistry, urinalysis, coagulation function test, and urine pregnancy test (only for women of childbearing potential);
- Weight measurement and Ccr calculation;
- Collect blood samples for exploratory analysis (one blood sample each for inflammatory indicators and PD biomarkers; among these, 5 mL of blood is collected for PD biomarker testing and sent to the central laboratory for testing);
- Exploratory skeletal muscle mass and function assessment: including ASMI, muscle strength (grip strength) and 6-meter walking speed test (specific test indicators are subject to the actual operation of each center). Among them, ASMI is detected and calculated by DXA, and the calculation formula is ASMI = appendicular muscle mass (kg) / height (m^2);
  - Return diary card;
- Return investigational product;
- MDS-UPDRS Part III score before the administration of background medication for PD (only applicable to subject who has received stable medication for PD within at least 4 weeks prior to study entry, and this score should be  $\geq$  12 hours from the most recent dose of background medication for PD);
- Take background medication for PD (only applicable to subject who has received stable medication for PD within at least 4 weeks prior to study entry);
- MDS-UPDRS score: Parts I, II, III, IV (if the subject has received stable medication for PD within at least 4 weeks prior to study entry, Part III score must be assessed at

$2 \pm 1$  hours after the administration of background medication for PD at this visit);

- Record concomitant medications/therapies;
- Record AEs;

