6.12.3. Laboratory Tests

Descriptive statistics will be performed for the results of hematology, blood biochemistry, coagulation function, and Ccr measurements at each visit, as well as their changes from baseline.

For the clinical significance assessment of hematology, blood biochemistry, urinalysis, and coagulation function, cross-tabulation will be used to summarize the changes in subjects' clinical assessment categories from baseline to the worst post-baseline clinical assessment category (clinically significant abnormality > abnormality without clinical significance > normal > not examined). Analyze the "urine white blood cells" and "urine sediment microscopic white blood cells" results in the clinical significance of urinalysis collectively, and analyze the "urine red blood cells" and "urine sediment microscopic red blood cells" results collectively.

List the hematology, blood biochemistry, urinalysis, coagulation function, and Ccr of the subjects. Tabulate all abnormal test results.

For laboratory tests, if the original result contains an equal sign(e.g., \leq , \geq), the numeric value will be directly used. If the original result contains only a less-than symbol, subtract 0.0001 from the numeric value. If the original result contains only a greater-than symbol, add 0.0001 to the numeric value.

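### The SAP gives the early-withdrawal visit no place among its analysis visits, so that visit's numeric safety values enter no by-visit table, and creatinine clearance (Ccr) measured there appears only in a listing

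*SAP*

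**What the plan says.** SAP 6.1 gives a closed list: "Analysis visits include: Baseline, V3 (Week 1 of treatment), V4 (Week 4 of treatment), V5 (Week 8 of treatment), V6 (Week 12 of treatment". Under its unscheduled-visit heading, the same section says: "For safety analysis tables summarized by visit, only scheduled visits are included". Unscheduled data are kept for baseline values, for listings, and for "Analyses involving abnormalities and clinically significant findings".

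Protocol 8.7.4 requires vital signs, physical examination, ECG, hematology, chemistry, urinalysis and coagulation at the early-withdrawal visit. It also requires "Weight measurement and Ccr calculation". Protocol 8.2.4 places Ccr at V1, V2, V3, V6 and early termination, so none is calculated at V4 or V5.

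SAP 6.12.3 plans three laboratory outputs:

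- By-visit statistics: "Descriptive statistics will be performed for the results of hematology, blood biochemistry, coagulation function, and Ccr measurements at each visit".
- A shift from baseline to the worst post-baseline category: "For the clinical significance assessment of hematology, blood biochemistry, urinalysis, and coagulation function, cross-tabulation will be used". Ccr is not named.
- A listing: "List the hematology, blood biochemistry, urinalysis, coagulation function, and Ccr of the subjects".

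SAP 6.12.4 to 6.12.6 plan the same kind of shift table for vital signs, physical examination and ECG. Protocol 2.5.1 counts "renal toxicity (basophilic lesions in renal tubules") among the main toxicities.

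**The concern.** A patient who leaves because of an adverse effect may have the most informative safety values at the withdrawal visit. Protocol 4.4 makes QTcF limits, hepatic limits and intolerable AEs grounds for withdrawal, so departure can be related to harm. If those values have no analysis visit, the Week 12 means come from patients who reached Week 12. The numeric change in those who left is then visible only by reading listings.

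Ccr is the clearest case. It has few scheduled time points and no worst-value table, yet it is the protocol's own measure of renal function for eligibility (exclusion criterion 8). The interval between the two treatment-period values is Day 7 to Day 84, which is most of the exposure.

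**Working it through.** The plan states no figure on this point, so the check follows each measurement from the withdrawal visit to the planned outputs.

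**Step 1. How the visit is classified.** The SAP does not say.

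- If the visit counts as unscheduled, SAP 6.1 keeps it out of by-visit safety tables.
- If it counts as scheduled, because it has its own column in Protocol 1.2, there is still no analysis visit to hold it and no window or mapping rule.
- Either way, its values reach no by-visit row. The closed list is what does this; the sentence on scheduled visits alone would not.
- SAP 6.2.2 gives the withdrawal visit and an unscheduled visit separate compliance rules. The authors therefore had the visit in view but wrote no matching rule in 6.1.

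**Step 2. Where the withdrawal values go.**

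| Measure | By-visit statistics | Worst-post-baseline shift | Listing |
|---|---|---|---|
| Hematology, chemistry, coagulation | No | Yes, by category | Yes |
| Urinalysis | None planned | Yes, by category | Yes |
| Vital signs, ECG | No | Yes, by category | Yes |
| Physical examination | None planned | Yes, by category | Yes |
| Ccr | No | Not planned | Yes |

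Ccr cannot be read into the chemistry row. SAP Table 1 lists it as a separate item, and the by-visit sentence in 6.12.3 names it beside biochemistry. The instruction in 6.12.3 to tabulate abnormal results does not help, because SAP 6.12.2 contrasts tabulation with summary and so uses the word for listings.

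**Step 3. Ccr over time.** The post-baseline values are Day 7, Day 84 and early withdrawal. A patient who leaves at Week 5 contributes the Day 7 Ccr to the by-visit table. The withdrawal Ccr, the only planned value after Week 1, is listed only.

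**Step 4. Scale, on assumed inputs.** The group size of about 50 is from SAP section 4. The withdrawal share d and the fall f in Ccr are assumptions. All withdrawals are taken to leave between V3 and V6 with a Ccr measured, and completers are taken to have a mean change of 0. Then:

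- patients whose last Ccr is listed only = 50 × d
- Week 12 row = 0, by construction
- mean of last post-baseline values = -d × f

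| d | Patients per group | f = 10 mL/min | f = 20 mL/min | f = 30 mL/min |
|---|---|---|---|---|
| 5% | 2.5 | -0.5 | -1.0 | -1.5 |
| 10% | 5 | -1.0 | -2.0 | -3.0 |
| 20% | 10 | -2.0 | -4.0 | -6.0 |

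**Step 5. Whether the creatinine category is a full substitute.** Take an assumed man of 75 years and 60 kg whose creatinine rises from 0.8 to 1.2 mg/dL. The formula is Cockcroft-Gault (Protocol Appendix II), read with 72 × creatinine as the denominator.

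- Before: (140 - 75) × 60 / (72 × 0.8) = 3900 / 57.6 = 67.7 mL/min
- After: 3900 / (72 × 1.2) = 3900 / 86.4 = 45.1 mL/min

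Ccr falls by 22.6 mL/min, one third of its starting value. If the site's reference range includes both creatinine values (an assumption), the shift table records normal to normal.

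**The case against.** The strongest reply is that renal information from withdrawals is reported elsewhere.

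- Serum creatinine and urea are chemistry items, so a withdrawal value can enter the biochemistry shift table.
- Chemistry is also taken at V4 and V5. The Week 5 patient therefore has a Day 28 creatinine in the by-visit table.
- A laboratory abnormality that changes study treatment or is clinically significant must be reported as an AE (Protocol 9.4.1.3). TEAEs leading to discontinuation and to early withdrawal are summarised by SOC and PT (SAP 6.12.2).
- Within a patient over 12 weeks, Ccr moves almost entirely with creatinine, plus any weight change.

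All of this stands. A reader might infer that renal harm in patients who leave is summarised nowhere, and the documents do not support that. What remains is that these routes give categories or event counts, depend on investigator judgement, and do not show the size of the Ccr change.

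The case for selective loss on renal grounds is also limited. Protocol 4.4 sets QTcF and hepatic limits but no Ccr limit. The tubular lesions came from the 4-week study in male rats, and the 13-week rat study reported no drug-related changes (Protocol 2.3.3.2).

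Finally, the withdrawal visit may fall up to 7 days after the investigator learns of the withdrawal, and mean steady-state half-lives are about 2.3 to 2.6 hours (Protocol 2.4.2). Many withdrawal values may be off drug. Repeat tests may also be waived when the previous visit was less than 7 days earlier. A row labelled as last on-treatment would therefore be wrong. The separate table templates (SAP 10.1) may settle some layout, but they are not part of the SAP text.

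**Conclusion.** The point holds as a gap in safety reporting. Followed exactly, the SAP puts no numeric value from the early-withdrawal visit into a by-visit safety table, and the withdrawal Ccr into no summary at all.

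Two stronger readings are tempting and should not be drawn:

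- **That by-visit tables show only patients who stayed on drug.** A patient who leaves at Week 9 still counts at V3, V4 and V5, and SAP 6.12.2 treats dose discontinuation and early withdrawal as separate categories. The correct description is patients still in the study at that visit.
- **That the safety tables as a whole are biased towards no effect.** The concern applies to observed-case means, and only where withdrawal is related to the measured harm. The shift and AE tables are not restricted in this way.

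The mean shifts of -0.5 to -6.0 mL/min are illustrations. The documents give no withdrawal rate and no human effect on Ccr, and the zero in the Week 12 row was assumed. The result that does not depend on assumptions is the trace in Steps 1 to 3.

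**What to change.** Before database lock, amend the SAP as follows.

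- **6.1:** State how the early-withdrawal visit is classified and which outputs use it.
- **6.12.3:** Add a summary of minimum post-baseline Ccr and its change from baseline by treatment group. Add a baseline-to-minimum table in numeric bands, with the protocol's own 30 mL/min entry limit as one boundary. Both should use early-withdrawal and unscheduled values. The bands need a separate table, because the existing cross-tabulation uses clinical-significance categories.
- **6.12.3 and 6.12.6:** For ALT, AST, TBIL, creatinine and QTcF, add a last post-baseline row and a worst post-baseline row (the maximum for these parameters), each with change from baseline and including early-withdrawal and unscheduled values. Label the first row last post-baseline, since the visit can follow the last dose. Where repeat tests were waived, the previous visit's value serves as the last one.

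The cost is SAP wording, a Ccr summary with its band table, and two rows for each of five parameters. No visit, test or data item is added. The tables become slightly longer.
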